### 5.2.1 DERIVATION OF THE PERFORMANCE GOAL FOR PATENCY

The Performance Goal was derived from a thorough literature review of trials with renal bare metal stent placement. Trials were identified by means of a PUBMED search of the English-language medical literature from 1991 to 2010. When available, the following data were extracted: author and year of publication, number of subjects, number of

arteries, restenosis definition, evaluation method, duration of follow-up, and restenosis rate. Of the 30 articles reviewed, 9 articles were excluded from the Performance Goal based on the following: results from studies with data collection from the 1980's which is not representative of today's standard of care, definitions used for restenosis were outside of our trial design, follow-up occurred at times outside of our assessments, and results from studies not yet published.

The following references were deemed relevant for the patency Performance Goal:

**Table 3: Derivation of Patency Performance Goal**

Author	Year	Number of Subjects	Number of Arteries	Evaluation Method	Follow-up Time	Restenosis Rate
Rocha -Singh et al 	2005	208	252	DUS	9 mo	17.4%
Laird et al 	2010	188	188	DUS	9-12 mo	16.8%
Fleming et al 	2010	30	66	Angio	6 mo	35%
Corriere et al 	2009	91	101	DUS	12 mo	26.7%
Rocha-Singh et al 	2008	100	117	DUS	9 mo	21.3%
Nolan et al 	2005	78	97	DUS	12 mo	25%
Nolan et al 	2005	82	96	DUS	12 mo	25%
Sapoval et al 	2005	52	52	Angio	6 mo	14%
Shammas et al 	2004	58	58	DUS, Angio, CTa	2-20 mo	26%
Lederman et al 	2001	300	358	Angio	16 mo	21%
Symonides et al 	1999	27	27	DUS, Angio to confirm	6 mo	30%
Van de Ven et al 	1999	42	51	Angio	6 mo	14%
Rundback et al 	1998	45	32	Angio	12 mo	25%
Tullis, et al 	1997	41	52	Angio/DUS	12 mo	44%
Harden et al 	1997	32	33	Angio	6 mo	12%
White et al 	1997	100	133	Angio	6-12 mo	19%
Iannone et al 	1996	63	86	DUS	12 mo	14%
Dorros et al 	1995	76	92	Angio	6 mo	25%
Hennequin et al 	1994	21	25	Angio	12 mo	19%

The weighted mean restenosis rate from these trials is 21.4%. Assuming a restenosis rate for PTRA of 40% as noted in Carr based on the analysis of 6 trials with PTRA and also used by Rocha-Singh, a restenosis rate of 30% leading to a Performance Goal for primary patency set at 70%. This goal will preserve at least 50% of the difference between the currently available bare metal stent rate and the PTRA rate, as well as adjust for a lesion set with a higher percentage stenosis (80%-100%) than previous reported studies (50%-100%).

## **5.3 ENDPOINT ANALYSIS AND REPORTING OF RESULTS**

### **5.3.1 GENERAL CONSIDERATIONS**

Unless otherwise specified, the following summary statistics will be presented. For continuous variables, statistics will include means, standard deviations and 95% confidence intervals for the means when normal-distribution assumptions are not violated. Otherwise, medians and Interquartile Range (IQR) will be presented. Categorical variables will be summarized using counts and frequencies. For time-to-event data, Kaplan-Meier estimates at the indicated time points will be displayed along with 95% confidence intervals. In addition, survival curves will be constructed for all time-to-event secondary endpoints using Kaplan-Meier methods.

Statistical tests relating to the primary endpoints will be one-sided with p-values less than 0.025 deemed significant.

Statistical analyses will be conducted in Statistical Analysis System (SAS) version 9.1 or above (SAS Institute, Cary, N.C.) or another validated statistical software package.

### **5.3.2 ANALYSIS POPULATIONS**

Intent-to-Treat (ITT) Analysis Set: All subjects enrolled in the study will be included in the ITT analysis set. This will be the primary analysis set.

Per Protocol Analysis Set: All subjects enrolled in the study, who receive the study device as intended with no major protocol violations (such as stent placement/deployment errors) will be included in the Per Protocol analysis set. The primary endpoints will be additionally tested in this analysis set.

### **5.3.3 MISSING DATA**

Results from imputing all possible combinations of successes and failures for the missing data will be summarized.

### **5.3.4 MULTIPLICITY ADJUSTMENT**

Alpha for the primary hypotheses will be controlled by testing the endpoints hierarchically. Patency will be tested first followed by systolic blood pressure. The test for systolic blood pressure will only be conducted if the patency Performance Goal is met.

Two additional secondary endpoints will be evaluated hierarchically if and only if the primary objective is met. In order to control alpha, the endpoint of clinically driven TLR will be tested as described below, followed by changes in the number or dosage of anti-hypertensive medications as compared to baseline.

### 5.3.5 PRIMARY ENDPOINT ANALYSIS

#### 5.3.5.1 PRIMARY PATENCY

The primary endpoint of primary patency will be summarized using counts and frequencies. An exact one-sided 95% confidence interval will be constructed and the upper limit compared to the Performance Goal of 70%. A p-value for the one-sided test of the difference between the observed rate and the Performance Goal will be presented.

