## 5.0 STATISTICAL CONSIDERATIONS AND ANALYSIS PLAN

### 5.1 ASSUMPTION OF PRIMARY ENDPOINT RATE

The endpoints will be tested in a sequential manner:

1) Functional Endpoint

Assessment of primary patency rate at 9-months, defined as continuous patency without the occurrence of a total occlusion of the original lesion, without a re-intervention to treat a partial or total occlusion of the stented segment, or bypass of the stented segment due to clinically-driven restenosis or occlusion.

Followed by:

2) Clinical Endpoint

Improvement in systolic blood pressure (SBP) at 9-months as compared to baseline systolic blood pressure.

If the null hypothesis for the functional goal is rejected at the 0.025 level of significance, the null hypothesis for the clinical goal will be tested at the 0.025 level. If rejected, success will be declared for both Performance Goals. Otherwise, if only the first (primary patency) null hypothesis can be rejected, success will be declared only for that Performance Goal. This sequential approach controls the overall significance level at 0.025. Of note, no success can be declared if the null hypothesis for the primary patency goal was not rejected, regardless of the outcome for the other Performance Goal.

For the primary patency endpoint, the proportion of subjects experiencing this outcome will be compared to the predefined Performance Goal of 0.70. Formally, the hypothesis to be tested is:

$H_0$ : The incidence  $p_{PP}$  of primary patency at 9-months is less than or equal to 0.70.

$H_0$ :  $p_{PP} \leq 0.70$

$H_A$ : The incidence  $p_{PP}$  of primary patency at 9-months is greater than 0.70.

$H_A$ :  $p_{PP} > 0.70$

The derivation of the Performance Goal is described in Section 5.2.1 Derivation of the Performance Goal for Patency.

For the SBP endpoint, the change between SBP from baseline to 9-month follow-up will be compared to a predefined Performance Goal of 10mmHg. Formally, the hypothesis to be tested is:

$H_0$ : The mean difference between SBP at 9-months and baseline,  $\mu_{\Delta\text{SBP}}$ , is less than or equal to 10mmHg.

$$H_0: \mu_{\Delta\text{SBP}} \leq 10\text{mmHg}$$

$H_A$ : The mean difference between SBP at 9-months and baseline,  $\mu_{\Delta\text{SBP}}$ , is greater than 10mmHg.

$$H_A: \mu_{\Delta\text{SBP}} > 10\text{mmHg}$$

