Both primary endpoints will be tested in one-sided fashion against a significance level of 0.025; the primary patency endpoint will be tested using exact binomial methods and the SBP endpoint will be tested using a paired t-test.

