## 5.2 SAMPLE SIZE

For a one-sided alpha of 0.025 and desired power of 87%, sample size for the primary patency endpoint is established by assuming a hypothesized primary patency incidence of 0.82, which gives 125 evaluable subjects therefore, accounting for 10% attrition, 138 subjects are needed for this endpoint. At the proposed evaluable sample size of 125, no more than 27 subjects (22%) can fail primary patency in order to meet the endpoint hypothesis.

For the endpoint of reduction in SBP, we assume an average reduction of 13.7mmHg. Under a hypothesized standard deviation of 12mmHg for a difference in SBP there will be 92% power to meet the Performance Goal. This standard deviation is conservatively approximated based on the expected range of SBP at baseline of 155mmHg to 180mmHg divided by 3 and assuming a similar standard deviation at the 9-month follow up. A mean difference in SBP at 9-months of 12mmHg will be required in order to reject the null hypothesis at a one-sided alpha of 0.025 at the proposed sample size.

The primary endpoints of primary patency and reduction in SBP are powered at 87% and 92%, respectively, in order to maintain the overall trial power at 80% to meet both endpoints.

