#### 5.3.5.2 SYSTOLIC BLOOD PRESSURE

The primary endpoint of SBP will be analyzed according to the Performance Goal of a decrease in SBP of 10mmHg.

The mean difference between SBP at 9-months and baseline will be compared to a fixed value of 10mmHg. The baseline SBP will be summarized for all subjects and for those subjects with 9-month follow-up data. The baseline and 9-month SBP data, as well as the difference in baseline will be summarized with means and standard deviations. A one-sided 95% confidence interval for the mean difference between baseline and 9-month SBP will be constructed and the limit will be compared to the 10mmHg Performance Goal. A p-value will be computed based on the paired t-test.

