9.9 Analysis of Primary Endpoints

Statistical tests relating to the primary endpoints will be one-sided with p-values less than 0.025 deemed significant.

Amendment #1: 15Jul13

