9.9.1. Primary Patency Analysis

The primary endpoint will be the cumulative incidence of primary patency at 9-months of study computed as the number of subjects with primary patency at 9-months divided by the number of subjects in the ITT population. An exact binomial one-sided 95% confidence interval will be constructed and the upper limit compared to the Performance Goal equal to 70%. A p-value for the one-sided exact test of the difference between the observed rate and the Performance Goal will be presented. The primary analysis will be analyzed with observed data only.

A planned subgroup analysis of the primary functional endpoint will be performed (details are provided in section 9.9.4

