9.9.2. Systolic Blood Pressure Analysis

The primary endpoint of SBP will be analyzed according to the Performance Goal of a decrease in SBP of 10mmHg.

The mean difference between SBP at 9-months and baseline will be compared to a fixed value of 10mmHg. The baseline and 9-month SBP data, as well as the difference in baseline will be summarized with means and standard deviations. A one-sided 95% confidence interval for the mean difference between baseline and 9-month SBP will be constructed and the upper limit will be compared to the 10mmHg Performance Goal. A p-value of the difference between the estimated SBP change from baseline and the Performance Goal will be computed using a paired t-test.

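### The patency interval is read at the wrong limit and the wrong confidence level, so it conflicts with the plan's own exact test at one-sided 0.025

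*Protocol*

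**What the plan says.** **Test.** Protocol 5.1 and SAP 5.7 set H0: patency ≤ 0.70 against HA: patency > 0.70. Protocol 5.1 ties success to the test: "If the null hypothesis for the functional goal is rejected at the 0.025 level of significance", the blood pressure goal is tested next. It adds: "Both primary endpoints will be tested in one-sided fashion against a significance level of 0.025", by exact binomial methods for patency and a paired t-test for SBP. SAP 9.9 keeps the threshold: "Statistical tests relating to the primary endpoints will be one-sided with p-values less than 0.025 deemed significant". Protocol 5.2 gives the matching cut-off at 125 evaluable: "no more than 27 subjects (22%) can fail primary patency in order to meet the endpoint hypothesis".

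**Patency interval.** Protocol 5.3.5.1: "An exact one-sided 95% confidence interval will be constructed and the upper limit compared to the Performance Goal of 70" per cent. SAP 9.9.1: "An exact binomial one-sided 95% confidence interval will be constructed and the upper limit compared to the Performance Goal equal to 70" per cent. Both sections then ask for a one-sided p-value against the same goal.

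**SBP interval.** Protocol 5.3.5.2: "A one-sided 95% confidence interval for the mean difference between baseline and 9-month SBP will be constructed and the limit will be compared" with the 10 mmHg goal. SAP 9.9.2: "A one-sided 95% confidence interval for the mean difference between baseline and 9-month SBP will be constructed and the upper limit" is to be compared with 10 mmHg.

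**Status.** SAP 2, 6.1, 6.2 and 8.7 record that enrolment ended at 68 subjects, that inferential results are to be read as descriptive, and that Type I error is no longer controlled.

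**The concern.** An interval supports the claim that patency exceeds 70% only if its lower limit lies above 70%. An upper limit above 70% says no more than that 70% has not been ruled out from below. The same sentence structure is used for clinically driven TLR (Protocol 5.3.6.2.1.1, SAP 9.10.1). There the upper limit is right, because TLR is a failure rate.

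The confidence level is a second, separate discrepancy. A one-sided 95% limit inverts a test at 0.05, not at 0.025. Correcting the side alone would still leave an interval that can pass when the test fails.

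At stake is a report that sets two comparisons with one goal side by side, for a co-primary endpoint, and lets them point in opposite directions. A reader could take an upper limit above 70% as meeting the goal.

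**Working it through.** **Inputs.** Goal 0.70, assumed patency 0.82, one-sided alpha 0.025, n = 125 evaluable, 10% attrition, SBP goal 10 mmHg, assumed reduction 13.7 mmHg, SD 12 mmHg (Protocol 5.1 and 5.2); 68 enrolled (SAP 6.1); 1.2 lesions per patient, from another trial (Protocol 2.1). Units are treated as independent.

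**Formulas**, for x patent of n:
- exact p = P(X ≥ x | n, 0.70)
- lower limit at level 1 − a = Beta quantile(a; x, n − x + 1)
- upper limit at level 1 − a = Beta quantile(1 − a; x + 1, n − x)

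The lower limit at level 1 − a exceeds 0.70 exactly when p < a, so a test at 0.025 pairs with a lower 97.5% limit.

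**Step 1: the plan's own cut-off.** At n = 125, P(X ≥ 98 | 0.70) = 0.0230 and P(X ≥ 97 | 0.70) = 0.0368. The smallest passing count at 0.025 is 98, that is 27 failures, as stated. Power is P(X ≥ 98 | 0.82) = 0.876, against the stated 87%.

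**Step 2: the interval rules at n = 125.**

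| Rule | Smallest x meeting it | Limit at that x | Probability of meeting it at true patency 0.70 |
|---|---|---|---|
| Upper 95% > 70% (limit and level as written) | 79 (63.2%) | 70.4% | 0.958 |
| Lower 95% > 70% (side corrected) | 97 (77.6%) | 70.6% | 0.0368 |
| Lower 97.5% > 70% (side and level corrected) | 98 (78.4%) | 70.15% | 0.0230 |

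At 78/125 the upper 95% limit is 69.6%. The sentence does not say which direction counts as success. If it were read as requiring an upper limit below 70%, it would be met only at 78/125 or fewer, with probability about 2 × 10⁻⁷ at true patency 0.82. Neither reading works.

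The lower 97.5% limit is 69.28% at 97/125 and 70.15% at 98/125, so the third rule returns the plan's cut-off. Interval and test then disagree under the second rule at one count only, 97.

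**Step 3: actual enrolment.** The number with 9-month data is not given, so a range is shown: 68 (none missing), 61 (68 × 0.9 = 61.2, the planned attrition), and 82 lesions (68 × 1.2 = 81.6, none missing).

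| n | Upper 95% > 70% from | Lower 95% > 70% from | Lower 97.5% > 70%, same as test at 0.025, from |
|---|---|---|---|
| 61 | 37 (60.7%) | 49 | 50 (82.0%) |
| 68 | 41 (60.3%) | 55 | 56 (82.4%) |
| 82 | 50 (61.0%) | 65 | 66 (80.5%) |

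**Step 4: SBP.** The smallest mean reduction that clears 10 mmHg is 10 + t(1 − a, n − 1) × 12/√n.
- n = 125, 95%: 10 + 1.657 × 1.073 = 11.78
- n = 125, 97.5%: 10 + 1.979 × 1.073 = 12.12 (the plan says 12; power at 13.7 is 0.928 against its 92%)
- n = 68, 95%: 10 + 1.668 × 1.455 = 12.43
- n = 68, 97.5%: 10 + 1.996 × 1.455 = 12.90

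A mean reduction between 11.78 and 12.12 at n = 125, or between 12.43 and 12.90 at n = 68, passes the interval and fails the test.

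**The case against.** The strongest reply is that no success rule rests on the interval. The documents only say the limit is compared. Success follows from rejecting H0 at 0.025, and the exact test, the p-value threshold and the 27-failure cut-off all agree. That stands: the test is not wrong, and 79/125 would matter only if someone judged success by the interval.

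Second, the SAP makes all inference descriptive, so no formal decision now depends on it. That also stands and lowers the stakes. But SAP 9.9.1 still orders the comparison and SAP 9.9 still calls p < 0.025 significant. In a descriptive report the interval is what readers look to.

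Third, SAP 8.1 plans two-sided 95% exact intervals for discrete variables, and the lower bound of such an interval is the one-sided 97.5% limit needed. This helps, but a correct interval elsewhere does not repair an explicit instruction to compare the wrong limit.

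Fourth, SAP 7.6.1 defines SBP change as 9-month minus baseline. On that scale an upper limit is the right side, against −10. True, but SAP 9.9.2 compares with +10 mmHg, and the hypotheses use +10, so the scale has to be stated.

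Last, the level mismatch alone is small: one count for patency and 0.35 to 0.48 mmHg for SBP. Agreed.

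**Conclusion.** The point holds. For patency, both documents name the wrong limit and a level that does not match the test. For SBP, the level does not match. The defect is two conflicting comparisons with the same goal beside a correct test, which makes this a wording error that should be fixed rather than a failure of the design.

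The side error is large if the interval is relied on: at n = 125 it separates 79 patent from 98. The level error on its own shifts the result by one patent unit. The n = 125 counts rest on independent units. The counts for 61, 68 and 82 also rest on the stated assumptions about missing data and lesions per patient. The SBP thresholds rest on the plan's SD of 12 mmHg.

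**What to change.** - **Patency (Protocol 5.3.5.1, SAP 9.9.1):** construct an exact one-sided 97.5% interval and compare its lower limit with 70%; the goal is met when that limit is above 70%. State the unit as the lesion, as Protocol 2.1 and SAP 7.6.1 and 8.8 require; SAP 9.9.1 currently counts subjects.
- **SBP (Protocol 5.3.5.2, SAP 9.9.2):** use the one-sided 97.5% level. Express the result as a reduction (baseline minus 9-month) and compare the lower limit with 10 mmHg. Note in SAP 7.6.1 that this is the sign-reversed change.
- **Subgroups (SAP 8.1):** align the one-sided 95% intervals for the primary endpoint rate in the same way.
- **TLR:** keep the upper limit. A 97.5% level there would follow only if the hierarchy in Protocol 5.3.4 is read as carrying 0.025. That is an inference, and SAP 9.10 drops the hierarchy.

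The cost is wording only, with no new data. Compared with a lower 95% limit, the corrected patency limit needs one more patent unit at n = 125, 61, 68 or 82. For SBP it needs 0.35 mmHg more mean reduction at n = 125 (12.12 against 11.78, before rounding) and 0.48 mmHg more at n = 68.

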#### 5.3.5.2 SYSTOLIC BLOOD PRESSURE

The primary endpoint of SBP will be analyzed according to the Performance Goal of a decrease in SBP of 10mmHg.

The mean difference between SBP at 9-months and baseline will be compared to a fixed value of 10mmHg. The baseline SBP will be summarized for all subjects and for those subjects with 9-month follow-up data. The baseline and 9-month SBP data, as well as the difference in baseline will be summarized with means and standard deviations. A one-sided 95% confidence interval for the mean difference between baseline and 9-month SBP will be constructed and the limit will be compared to the 10mmHg Performance Goal. A p-value will be computed based on the paired t-test.

### 5.3.6 ADDITIONAL ANALYSES

#### 5.3.6.1 SENSITIVITY ANALYSIS

For primary patency, a tipping point analysis will be conducted in order to assess the effect of missing data on the analysis. Results from imputing all possible combinations of successes and failures for the missing data will be summarized.

For the SBP endpoint, as a best/worst case analysis, the largest/smallest drop in SBP seen in the complete data will be filled in for the missing values. Summary statistics for the resulting mean difference and p-values from the primary hypothesis test will be presented. In addition, multiple imputations will be used by substituting imputed SBP at 9-months based on available baseline characteristics (including baseline SBP) and then recalculating the mean differences, presenting summary statistics and the p-value for the primary hypothesis.

#### 5.3.6.2 SECONDARY ENDPOINTS ANALYSIS

##### 5.3.6.2.1 MAJOR SECONDARY ENDPOINTS

###### 5.3.6.2.1.1 TLR

The secondary endpoint of clinically driven TLR will be summarized using counts and frequencies. An exact one-sided 95% confidence interval will be

constructed and the upper limit compared to the Performance Goal rate of 8.5% as described below. A p-value for the one-sided test of the difference between the observed rate and the Performance Goal will be presented.

The Performance Goal of 8.5% was established from a review of the relevant literature as detailed in the following table.

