9.10.1. TLR

The secondary endpoint of clinically driven TLR will be summarized using counts and frequencies. An exact binomial one-sided 95% confidence interval will be constructed and the upper limit compared to the Performance Goal rate of 8.5%. A p-value for the one-sided test of the difference between the observed rate and the Performance Goal will be presented.

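### Protocol 5.3.4 puts clinically driven TLR in the alpha-controlled hierarchy without giving it a level, and its only decision rule is a nominal 0.05 test following a chain run at one-sided 0.025

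*Protocol*

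**What the plan says.** **Protocol, primary chain.** Section 5.1 tests patency and then systolic blood pressure (SBP), each at one-sided 0.025, and concludes: "This sequential approach controls the overall significance level at 0.025". Section 5.3.1 sets the p-value threshold: "Statistical tests relating to the primary endpoints will be one-sided with p-values less than 0.025 deemed significant".

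**Protocol, extension to secondaries.** Section 5.3.4 adds: "Two additional secondary endpoints will be evaluated hierarchically if and only if the primary objective is met". It continues: "In order to control alpha, the endpoint of clinically driven TLR will be tested as described below", with the change in antihypertensive medication following TLR. No level is given for either step.

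**Protocol, the TLR rule.** Section 5.3.6.2.1.1 begins "The secondary endpoint of clinically driven TLR will be summarized using counts and frequencies. An exact one-sided 95% confidence interval will be" and goes on "constructed and the upper limit compared to the Performance Goal rate of 8.5% as described below". It then says: "A p-value for the one-sided test of the difference between the observed rate and the Performance Goal will be presented". No threshold is attached to that p-value.

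**SAP.** Section 9.10.1 keeps the same comparison: "An exact binomial one-sided 95% confidence interval will be constructed and the upper limit compared to the Performance Goal rate of 8.5" percent. However, enrollment stopped at 68 subjects (SAP 6.1). SAP 2 and 6.2 make all inference descriptive and exploratory, SAP 8.7 drops type I error control, and SAP 9.10 drops the hierarchy for secondary endpoints. SAP 8.1 sets two-sided 95% exact intervals for discrete variables.

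**The concern.** A fixed sequence protects a family at a given level only if every step is tested at that level. Here the two gates are run at 0.025, and the third step is decided on a limit that corresponds to 0.05. The protocol says that the ordering is there to control alpha, but does not say at what value once TLR is included.

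The one-sided 95% wording also appears for patency (5.3.5.1) and SBP (5.3.5.2). For those two endpoints, 5.1 and 5.3.1 supply an explicit 0.025 rule that can govern. TLR has nothing to fall back on, because the 5.3.1 threshold is confined to the primary endpoints and the TLR p-value is only to be presented. Correcting the co-primary intervals alone would leave TLR as it is.

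TLR is the only secondary endpoint with a performance goal. A borderline count would meet that goal under one reading of the protocol and miss it under the other.

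**Working it through.** **1. Which alpha the design uses.** Inputs from protocol 5.2: n = 125 evaluable, goal 0.70, assumed patency 0.82, one-sided alpha 0.025, power 87%, at most 27 failures.

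Exact binomial: find the smallest r with P(X ≥ r | 125, 0.70) ≤ alpha. Power is P(X ≥ r | 125, 0.82).
- alpha 0.025: r = 98, so at most 27 failures; size 0.0230, power 87.6%. This reproduces the protocol.
- alpha 0.05: r = 97, so at most 28 failures; size 0.0368, power 91.6%. This does not.

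The SBP figures also match 0.025. With n = 125, SD 12, true reduction 13.7 and goal 10 mmHg, power is 92.8% and the required mean is 12.1 mmHg (protocol: 92% and 12 mmHg). The primary chain is therefore built on 0.025, and a one-sided 95% limit does not correspond to it.

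**2. The TLR rule.** The documents give no sample size, power or critical count for TLR, so n is an assumption: 125 (planned evaluable) or 138 (planned enrolled). With x events, p = P(X ≤ x | n, 0.085). The exact (Clopper-Pearson) one-sided upper limit at level 1 − a is the (1 − a) quantile of Beta(x + 1, n − x). The limit falls below 8.5% exactly when p < a.

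| n | TLRs | p | 95% upper limit | 97.5% upper limit |
|---|---|---|---|---|
| 125 | 4 | 0.0159 | 7.17% | 7.99% |
| 125 | 5 | 0.0403 | 8.23% | 9.09% |
| 138 | 5 | 0.0199 | 7.47% | 8.25% |
| 138 | 6 | 0.0461 | 8.40% | 9.22% |

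The pass mark is 5 against 4 events at n = 125, and 6 against 5 at n = 138. The exact size of the 95% rule is 0.0403 or 0.0461. Relative to 0.025 that is 0.0403/0.025 = 1.6 and 0.0461/0.025 = 1.8.

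**3. How often the choice would matter.** If the true TLR rate is 3%, 4% or 5% (assumed), the chance of exactly 5 events in 125 is 14.7%, 17.9% or 15.6%.

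**4. Family error.** If a primary null is true, a false TLR claim first requires a false primary success, so the gate holds it to 0.025. If both primary nulls are false, the gate can open with probability near 1, and the bound is the size of the TLR step: 0.05 nominal, 0.040 to 0.046 exact.

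**5. Under the SAP.** SAP 7.6.2 divides by subject-lesions in the ITT population, and ITT is all enrolled (SAP 9.3). The lesion count is not given, so it is an assumption. At one lesion per subject it is 68. At the 1.2 lesions per subject cited in SAP 5.2 it is 68 × 1.2 ≈ 82.
- 68 to 71 lesions: both limits allow at most 1 event, so they agree.
- 72 to 82 lesions: they differ at 2 events. At 82, p = 0.0256 and the limits are 7.48% and 8.53%.

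**The case against.** **No level is stated for TLR.** A reader might infer that TLR is claimed at twice a stated error rate. The documents do not support that wording. The 0.025 sentence in 5.1 closes a paragraph about patency and SBP only, and 5.3.1 limits its threshold to primary endpoints. Carrying 0.025 forward to TLR is an inference from 5.3.4. A factor of two is also only nominal; the exact factor is 1.6 to 1.8 at the planned size. This narrows the point without removing it: a step said to control alpha with no alpha stated needs correcting on either reading.

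**The SAP withdrew the claim.** This stands. Under the SAP there is no controlled family for TLR to breach, so one cannot infer that the SAP's TLR result inflates a family error rate. Adding a p < 0.025 pass rule to SAP 9.10.1 would restore a confirmatory decision that the SAP removed. The SAP's two-sided 95% exact interval also already has the 97.5% limit as its upper end. What remains is that SAP 9.10.1 still sets a one-sided 95% limit beside 8.5%, which invites a met-or-missed reading.

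**The choice may not matter at the size reached.** With 68 to 71 lesions it does not. A count based on fewer than 68 evaluable subjects would not be the SAP's analysis.

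**It overlaps the co-primary intervals.** The wording fault is shared and should be corrected together, but only TLR lacks a separate threshold.

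**Conclusion.** The point holds for the protocol. TLR is placed in an alpha-controlling sequence without a level, and its sole decision rule is a nominal 0.05 test after steps run at 0.025. With both primary nulls false, the chance of a false TLR claim is bounded by 0.05. At the planned size the verdict turns on a single count, and the pass mark moves by one event. This rests on exact binomial testing against 8.5% and on TLR being analysed in 125 or 138 subjects.

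For the SAP the point is one of presentation only. Whether the two limits could disagree depends on a lesion count that the documents do not report.

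**What to change.** **Protocol 5.3.6.2.1.1.** Replace the one-sided 95% limit with a one-sided 97.5% exact upper limit, and state that the TLR goal is met only if the exact one-sided p-value against 8.5% is below 0.025. State the level in 5.3.4 as well, and cover the medication step there, since it has none either. Align the confidence level of the intervals in 5.3.5.1 and 5.3.5.2 in the same edit.

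**SAP 9.10.1.** Add no pass/fail rule. Replace the one-sided 95% limit with the two-sided 95% exact interval from SAP 8.1, and label the comparison with 8.5% as descriptive.

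**Cost.** A few lines of wording, no new data and no change in sample size. Under the protocol the pass mark becomes 4 of 125 instead of 5, or 5 of 138 instead of 6. At n = 125 and an assumed true TLR rate of 3%, 4% or 5%, the chance of meeting the goal falls from 82.6%, 61.6% or 40.1% to 67.8%, 43.7% or 24.6%.
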